6 SAMPLE SIZE JUSTIFICATION

Assuming that 40% of the placebo subjects will be improving (by chance) without any intervention, a total sample size of 118 (dosed with randomized study treatment), 59 per treatment arm (after randomization), would provide approximately 80% power to detect a 30% difference between the treatment arm and placebo arm in proportion of subjects with any improvement in GI severity, as measured by the average change from Day 0 in GSRS score to Day 10. Power was estimated assuming a 15% early discontinuation rate.

7 STATISTICAL ANALYSIS METHODS

The statistical software, SAS[®], will be used for all summaries and statistical analyses.

Summary statistics will be used throughout. For continuous endpoints, the summary statistics will generally include: the number of subjects with data, mean, standard deviation (SD), median, 25th and 75th percentile (Q1, Q3), minimum and maximum. For categorical endpoints, the summary statistics will generally include: number of patients randomized and dosed, the number of patients with data, and the number and percent of subjects with data in each category.

All statistical tests will be 2-sided with a type I error rate of 5%, unless otherwise specified.

7.1 Analysis population

7.1.1 Modified ITT population

The modified intent-to-treat (modified ITT) population consists of all patients who were randomized, received at least one dose of DMF treatment, received at least one dose of study treatment (Montelukast or placebo) on/after the first DMF dose date, and had at least one GSRS score measurement during the Day 1 - Day 10 period.

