12. WITHDRAWAL OF SUBJECTS FROM STUDY TREATMENT **AND/OR THE STUDY**

A subject *must* permanently discontinue study treatment and be withdrawn from the study for any of the following reasons:

- Failure to meet the required eDiary compliance criteria (\geq 75%) in the 14 days prior to randomization.
- Failure to meet the GSRS score criteria during the DMF-GI Monitoring Period. •
- The subject experiences a medical emergency that necessitates permanent discontinuation of study treatment.
- The subject uses prohibited concomitant medications (as outlined in Sections 1 and 10.3.1).
- The subject withdraws consent.

Protocol 109MS414

- At the discretion of the Investigator for medical reasons or for noncompliance.
- The subject has a concurrent illness or injury, or abuses alcohol or drugs to the extent that, in the judgment of the Investigator and/or Sponsor, it would affect assessments of clinical status to a significant degree.

The reason for discontinuation of study treatment and withdrawal from the study must be recorded in the subject's CRF.

Subjects who discontinue study treatment will be withdrawn from the study. Whenever possible, subjects who prematurely discontinue study treatment should complete an ET Visit (undergoing the same assessments as the Week 10 Visit).

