16.4. Efficacy Data

16.4.1. Analysis Population

The intent-to-treat (ITT) population defined below will be used for the efficacy analysis.

The ITT population is defined as all randomized subjects who receive at least 1 dose of randomized study treatment (montelukast or placebo).

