7.2 Study subjects

7.2.1 Analysis population

Unless otherwise stated, the analysis population for the efficacy analyses will be the modified ITT population. Safety analyses will be summarized in the Montelukast/placebo safety analysis population, while selected outputs will be performed in the DMF safety analysis population.

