7.2.2 Accounting of Subjects

The following subject categories will be summarized for this study using numbers and percentages based on all patients enrolled in the study:

- Number of subjects randomized
- Number of subjects who were dosed with DMF (DMF safety analysis population)
- Number of subjects dosed with study treatment (modified ITT population, Montelukast/placebo safety analysis population)
- Number of subjects completed study treatment
- Number of subjects discontinued study treatment
 - Reason for study treatment discontinuation
- Number of subjects continuing DMF at the Week 10 visit
- Number of subjects discontinued DMF by Week 10 or at Week 10
 - Reason for DMF treatment discontinuation
- Number of subjects completed the study
- Number of subjects withdraw from the study
 - Reason for study withdrawal

Subjects who discontinued treatment or withdrew from the study and the reasons for discontinuation or withdrawal will be listed. In certain cases, case report form (CRF) text detailing the reasons for discontinuation may suggest additional clarification of the reason provided on the CRF. Therefore, additional information for subject accounting may be presented, utilizing reasons for discontinuing treatment from the study reclassified based on the detailed CRF text.

7.2.3 **Protocol Deviations**

Protocol deviations identified in the study will be listed.

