Average change of GSRS score from baseline (Day 0) to Week 1, 2, 3, 4, 5, 6 and 8 will be summarized; a repeated measures model for the change of the GSRS score from baseline, adjusted for age, weight and baseline GSRS score, will be used to estimate effect at each time point. Sensitivity analyses using ANCOVA model for the average change may be performed.

Average change of GSRS score from Day 0 to 72 hours from the initiation of randomized study treatment

Average change of GSRS score from baseline (Day 0) to 72 hours (Day 3) from the initiation of randomized study treatment will be summarized and analyzed by the repeated measures method. No sensitivity analysis will be performed.

Proportion of subjects who take GI symptomatic therapy during the study

From Day 10 onward, subjects are allowed to use symptomatic therapy to treat DMFrelated GI events. The proportion of subjects who take GI symptomatic therapy from Day 10 to Week 10 will be summarized by treatment and analyzed using the Chi-squared test.

[figure not shown]
Percentage of subjects who discontinue DMF therapy due to the GI-related adverse events from Day 0 to Week 10

The proportion of subjects who discontinue DMF due to the GI-related adverse events from Day 0 to Week 10 will be summarized by treatment and analyzed using the Chi-squared test.

Proportion of subjects who experience flushing events

The proportion of subjects who experience flushing events from Day 0 to Week 10 will be summarized for the modified ITT population by treatment group and analyzed using the Chi-squared test. Flushing event as defined as an event coded to any of the following preferred terms: Flushing, Hot flush (under SOC of Vascular disorders), Erythema, Generalized erythema, Skin burning sensation (under SOC of Skin and subcutaneous tissue disorders), Burning sensation (under SOC of Nervous system disorders), Feeling hot (under SOC of General disorders and Administration site conditions), Hyperaemia (under SOC of Vascular disorders).

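### The SAP tests DMF discontinuation and flushing only in dosed subjects with a Day 1-10 GSRS score, so a subject who stops straight after the first dose can drop out of the comparison

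*Combined protocol and SAP*

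**What the plan says.** Protocol 16.4.1 sets the efficacy population without any diary condition: "The ITT population is defined as all randomized subjects who receive at least 1 dose of randomized study treatment (montelukast or placebo").

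SAP 7.1.1 defines a modified ITT population instead. It requires randomization, a DMF dose, a dose of montelukast or placebo on or after the first DMF dose, "and had at least one GSRS score measurement during the Day 1 - Day 10 period". SAP 7.2.1 applies it widely: "Unless otherwise stated, the analysis population for the efficacy analyses will be the modified ITT population".

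Two secondary endpoints in SAP 7.3.4 count events from Day 0 and do not use the GSRS:

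- DMF discontinuation: "The proportion of subjects who discontinue DMF due to the GI-related adverse events from Day 0 to Week 10 will be summarized by treatment", with a chi-squared test. No population is named, so the default applies.
- Flushing over the same period: it "will be summarized for the modified ITT population by treatment group and analyzed using the Chi-squared test".

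The subject accounting in SAP 7.2.2 has one line for "Number of subjects dosed with study treatment (modified ITT population, Montelukast/placebo safety analysis population"), although 7.1.1 and 7.1.2 define these two populations differently.

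**The concern.** The GSRS condition is met or failed after dosing, and the reason for failing it can be the outcome itself. The subjects most likely to have no Day 1-10 score are those who stop at once. For an endpoint that counts stopping DMF because of GI events, that is a selection on the event. It can fall unequally on the two arms, and nothing in the plan says in which direction.

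Reducing GI discontinuations is the first secondary objective listed in protocol 6.1.2 and SAP 2.2. Few events are expected, so each one carries weight.

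**Working it through.** The plan gives no figure for this point. Its sample size of 118 is for the primary endpoint and does not enter here. The check has two parts.

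**Can the excluded case arise?**

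1. The eDiary alert tells the subject to start the tablets the same day (protocol 7.2.4, 9.2), and montelukast is taken in the evening (protocol 10.1.2.1).
2. Under SAP 2.1, if the first dose falls on the day the threshold is reached, that day is Day 0. That day's diary entry is therefore not a Day 1-10 score.
3. Protocol Section 12: "Subjects who discontinue study treatment will be withdrawn from the study". The schedule of events has the eDiary returned on discontinuation.
4. So a subject who follows the alert, takes one tablet and then stops everything can have no Day 1-10 score.
5. The event is still recorded. Protocol 15.2.1 requires GI AEs leading to permanent discontinuation or withdrawal to be recorded, and puts flushing on the CRF. Neither depends on the diary score.
6. The DMF-discontinuation window opens at Day 0, so this subject is an event under 7.3.4 and is excluded under 7.1.1.

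The route is narrow. One score on any of the ten days keeps the subject in. If the first dose is taken the day after the threshold, SAP 2.1 makes the day before dosing Day 0, and an entry on the dosing day qualifies.

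**How much could it move the result?**

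Inputs:
- Dosed subjects: enrollment closes at about 60 (SAP 5). With 1:1 allocation (protocol 9.2) this is taken as 30 per arm.
- Background rate: at most 5% of DMF-treated subjects discontinued for GI events in pooled Phase 2 and 3 data (protocol 5.2). Used here as an assumption.
- Dosed subjects with no Day 1-10 score: not given. Assumed 0 to 2 per arm.

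Expected events per arm: 0.05 × 30 = 1.5. At the planned 59 per arm: 0.05 × 59 = 2.95.

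An arm with two events among 30 dosed:

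| Events lost | Events/N | Rate |
|---|---|---|
| 0 | 2/30 | 6.7% |
| 1 | 1/29 | 3.4% |
| 2 | 0/28 | 0% |

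At 59 per arm, losing one of two turns 2/59 (3.4%) into 1/58 (1.7%).

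Effect on the difference, 30 per arm, montelukast against placebo:
- True 1/30 against 3/30: 10.0 − 3.3 = 6.7 points. One placebo event lost gives 1/30 against 2/29: 6.9 − 3.3 = 3.6 points.
- True 3/30 against 3/30: no difference. One montelukast event lost gives 2/29 against 3/30: 10.0 − 6.9 = 3.1 points in favour of montelukast.

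Effect on the test (uncorrected chi-square, 30 per arm):
- With no events in one arm, 0 against 3 gives p = 0.076. For 0 against 4, chi-square = 60 × (30 × 4)² / (30 × 30 × 4 × 56) = 4.29, above 3.84. Four events are 13% of an arm.
- A change across 0.05 can be built, but only at high rates: 1/30 against 6/30 gives p = 0.044, and 1/30 against 5/29 gives p = 0.077. Here 6/30 is 20%, four times the background ceiling.

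**The case against.** The best case for leaving the text alone has several parts.

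- **Few subjects, possibly none.** Exclusion needs ten days without a score, in subjects who met 75% diary compliance before randomization and whose dosing was itself triggered by a diary entry. This stands. A reader might infer that a subject could be lost before any diary entry; that cannot happen in a subject dosed on the alert. Only the absence of Day 1-10 entries matters.
- **The stop is reported elsewhere.** It would appear in the accounting of DMF discontinuations with reasons, in Listing 1 and in Table 35.2. SAP 7 also says categorical summaries will generally show numbers dosed and numbers with data. This stands: the event does not vanish from the report. It is missing from the between-arm test. The protocol planned only a summary of this endpoint; the SAP added the test.
- **GI symptomatic therapy.** A reader might extend the point to this endpoint, which has the same default population. The documents do not support that, because "The proportion of subjects who take GI symptomatic therapy from Day 10 to Week 10 will be summarized by treatment". An immediate quitter is withdrawn before that window and would enter an all-dosed analysis only as a non-event. No change is claimed there.
- **Flushing is the weaker case.** A subject who stops for GI symptoms need not have flushed, and Table 33.1 gives AEs by preferred term in all dosed subjects. This is fair. But flushing is counted from Day 0 and can precede the stop, and Table 33.1 does not give the combined flushing definition of 7.3.4.
- **The protocol set is not full ITT either.** About 118 of 295 randomized subjects are expected to be dosed. True, so it would be too strong to say that the SAP gives up a full intent-to-treat comparison. The difference is timing: the threshold is reached before any blinded tablet is taken, whereas the GSRS condition is applied afterwards.
- **The DMF-dose condition would be dropped.** The threshold is assessed on DMF, so anyone dosed per protocol has already taken it. The difference is negligible.

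A reader might also infer that the exclusion could decide the significance of the test. At about 1.5 expected events per arm it could not; the example above needs a 20% rate.

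**Conclusion.** The point holds for DMF discontinuation due to GI events and, with less force, for flushing. The SAP adds a post-dose condition that neither endpoint needs, departs from the protocol's efficacy population, and can remove an event from the test meant to count it.

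The size is unknown. With an assumed loss of one of two events at about 30 per arm, the observed rate halves, from 6.7% to 3.4%; with no affected subjects there is no effect. The 5% background rate is for discontinuation over the whole of earlier studies (two years of treatment in Phase 3). It is not a rate of stopping right after a first tablet, so it bounds nothing about how many are excluded. This is a worthwhile, inexpensive correction to a secondary analysis and does not threaten the primary result.

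The single line in 7.2.2 is a labelling fault, but it bears on the point: if read as one count, it hides how many dosed subjects were excluded.

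**What to change.** - In SAP 7.2.1 and 7.3.4, state that DMF discontinuation due to GI AEs (Table 27) and flushing (Table 28) are analysed in all randomized subjects with at least one dose of montelukast or placebo, by randomized arm. This is the protocol 16.4.1 set.
- Keep the Day 1-10 GSRS condition for the endpoints built on GSRS scores. Leave GI symptomatic therapy (Table 26) as it is on this account.
- In SAP 7.2.2, give the dosed count and the modified ITT count on separate lines by arm, with the reason for each exclusion.

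The cost is SAP wording and two efficacy denominators in the report, which need clear table footnotes. No new data are required: SAP 7.1.2 already defines an all-dosed safety population. If no dosed subject lacks a Day 1-10 score, the results do not change.

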7.1.2 Safety population

Montelukast/placebo safety analysis population

The primary safety analysis population consists of all patients who received at least 1 dose of randomization study treatment (Montelukast or placebo).

DMF safety analysis population

The DMF safety analysis population will consists of all patients who received at least 1 dose of DMF. Selected analyses will be presented in the DMF safety analysis population.

7.1 Analysis of baseline data

Baseline GSRS score is defined as the score collected at Day 0.

Baseline data of demographics and disease characteristics are defined as data collected at the Screening visit. If there is more than one value on or before the screening visit, the Baseline value will be selected from all measurements collected before or on the date of the screening visit; the value closest to the date of screening visit will be used as the Baseline value.

Definition of baseline value for clinical laboratory data

Tecfidera baseline value

The Tecfidera baseline value is defined as the measurement collected before or on the date of the Randomization visit. If there is more than one value on or before the Randomization visit date, then the Tecfidera baseline value will be selected from all measurements collected before or on the date of the Randomization visit; the value closest to the date of Randomization visit will be used as the Tecfidera baseline value.

Montelukast baseline value

The Montelukast baseline value is defined as the measurement collected before or on the date of first dose of Montelukast /placebo. If there is more than one value on or before the first dose date of Montelukast /placebo, then the Montelukast baseline value will be selected from all measurements collected prior to or on the date of the first dose of Montelukast/placebo; the value closest to the date of the first dose date will be used as the Montelukast baseline value.

7.2 Study subjects

7.2.1 Analysis population

Unless otherwise stated, the analysis population for the efficacy analyses will be the modified ITT population. Safety analyses will be summarized in the Montelukast/placebo safety analysis population, while selected outputs will be performed in the DMF safety analysis population.

7.2.2 Accounting of Subjects

The following subject categories will be summarized for this study using numbers and percentages based on all patients enrolled in the study:

- Number of subjects randomized
- Number of subjects who were dosed with DMF (DMF safety analysis population)
- Number of subjects dosed with study treatment (modified ITT population, Montelukast/placebo safety analysis population)
- Number of subjects completed study treatment
- Number of subjects discontinued study treatment
 - Reason for study treatment discontinuation
- Number of subjects continuing DMF at the Week 10 visit
- Number of subjects discontinued DMF by Week 10 or at Week 10
 - Reason for DMF treatment discontinuation
- Number of subjects completed the study
- Number of subjects withdraw from the study
 - Reason for study withdrawal

Subjects who discontinued treatment or withdrew from the study and the reasons for discontinuation or withdrawal will be listed. In certain cases, case report form (CRF) text detailing the reasons for discontinuation may suggest additional clarification of the reason provided on the CRF. Therefore, additional information for subject accounting may be presented, utilizing reasons for discontinuing treatment from the study reclassified based on the detailed CRF text.

7.2.3 **Protocol Deviations**

Protocol deviations identified in the study will be listed.

7.2.4 Demographic and Baseline Characteristics

Demographic data, including age (years), age category ($\leq 40, > 40$) and gender will be summarized. In addition, baseline height, weight, body mass index (BMI), systolic blood pressure, diastolic blood pressure and temperature will also be summarized.

Baseline disease characteristics will also be summarized using descriptive statistics. These include years since disease (MS) onset, years since diagnosis, days from the most recent pre-study relapse, total number of relapses in the past 12 months, 2 years and 3 years and Baseline EDSS score.

7.2.5 MS Treatment History

MS treatment prior to the study will be summarized by the type of approved therapy. Number and percentage of patients with a particular approved therapy will be presented.

7.2.6 Medical History

Medical history and MS disease history will be summarized as the number and percentage of patients with history of a medical condition in each body system.

7.2.7 Extent of Exposure and eDiary Compliance

Montelukast/placebo treatment exposure and compliance

The total number of days on study treatment (Montelukast or placebo) will be summarized for the modified ITT population. The number of days on study treatment is calculated as the number of days from the date of the first dose of the study treatment (Montelukast or Placebo) to the date of the last dose of study treatment, plus 1.

In addition, the number of doses of study treatment taken between Day 0 and Day 10 will be summarized for the modified ITT population.

Study treatment compliance rate will also be summarized in the modified ITT population. Study treatment compliance rate will be defined as the total number of study treatment doses taken divided by the total number of study treatment doses expected to be taken. Study treatment compliance will be summarized in each of the following periods:

- From Day 0 to Day 10
- From Day 0 to Week 8

DMF treatment exposure and compliance

In the DMF safety analysis population, the total number of days on DMF will be summarized. The number of days on DMF is calculated as the number of days from the date of the first dose of DMF after randomization to the date of the last dose of DMF, plus 1.

In addition, the number of doses of DMF taken between Day 0 and Day 10 will be summarized for the modified ITT population.

The DMF compliance rate will also be summarized. The DMF compliance rate will be defined as the total number of DMF doses taken divided by the total DMF doses expected to be taken during the period. DMF compliance will be summarized in the modified ITT population in each of the following periods:

- From the randomization visit to Week 10
- From the randomization visit to Day 0
- From Day 0 to Day 10
- From Day 0 to Week 10

Time on study

Time on study, based on the number of days from the date of the first dose of DMF to the last date on study plus 1, will also be summarized, for the Montelukast/placebo safety analysis population. The last known date on the study will be taken as the last visit/evaluation date from all relevant data for a subject.

GSRS compliance

GSRS score compliance rate will be summarized in the modified ITT population. GSRS score compliance rate will be defined as the total number of days when the GSRS score is recorded divided by the total number of days when the GSRS score is expected to be recorded. GSRS score compliance will be summarized in each of the following periods:

- From Day 0 to Day 10
- Form Day 0 to Week 10

7.2.8 Concomitant Medications

Concomitant medications, any drug or substance administered on or after the day of the first dose of DMF will be summarized. Concomitant medications will be coded using the World Health Organization (WHO) drug dictionary.

Data on concomitant medications treating for GI symptoms are collected in the eDairy. Data on concomitant medications treating for non-GI symptoms are collected in the CRF. Number and percentage of patients taking concomitant medication will be summarized.

7.3 Efficacy Analysis

7.3.1 Analysis Population

The primary analysis population will be the modified intent-to-treat (modified ITT) population defined in 7.1.1.

